6.4.3. Vital Sign Assessments

Vital signs assessments will be made which include blood pressure (BP), pulse, respiration rate and oral body temperature. The results for each individual's measurements will be recorded in the CRF. See Section 6.1.5. above for further details.

6.4.4. Nasal Examination

Nasal examination will be performed (Visit 2, Day 8). The Investigator will perform a thorough examination of the nasal mucosal surfaces for presence of nasal diseases likely to affect deposition of intranasal treatment or any superficial or moderate nasal mucosal erosion, nasal mucosal ulceration, or nasal septum perforation. Any clinically relevant (new or worsening) findings will be noted in the adverse event CRF page.

6.4.5. Pregnancy Test

All women of childbearing potential will have a urine pregnancy test. It will be conducted at the site using a urine dipstick. Results from the pregnancy test will be recorded in the CRF. See Section 7.7. for more information.

6.4.6. Return of Study Treatment Devices and Subject E-diary

The site personnel will collect the subject e-diary and all used and unused study treatment from the subjects. Comments related to breakage, replacement of devices and treatment compliance (visual verification) will be recorded in the CRF.

Document Name	CCI	Protocol B_Final_Amendment 4_Clean_QA Review	
Type	Version	Document Identifier	Effective Date
elido_clinical_doc	1.0; CURRENT; Most-Recent; Effective	090032d580d43d4b	19-May-2017 09:57:58
Reason For Issue	Auto Issue		

6.4.7. Concomitant Medication

Any changes in concomitant medication or non-drug treatments/procedures will be recorded in the CRF.

6.4.8. Safety Monitoring

The occurrence of any SAEs related to study participation will be recorded beginning at the time the subject provides written informed consent. AEs and SAEs will be collected from the start of the investigational product. This information should be recorded in the Investigator's source documents or in the subject's e-diary if they are not at the study site. If the AE meets the criteria of an SAE, it must be reported to GSK. All adverse events will be treated appropriately and the action taken to treat the AE should be recorded on the Adverse Event CRF page. See Section 7.2. for further details.

6.4.9. Early Termination/ Premature Subject Withdrawal

Subjects may voluntarily discontinue study treatment for any reason at any time. Study treatments also must be discontinued for any subject whose treatment code has been broken inadvertently or for any emergency or non-emergency reason. If premature withdrawal occurs for any reason, the Investigator must determine the primary reason for a subject's premature withdrawal from the study and record this information in the CRF. Subjects, who discontinue study treatment before completing the study and those who prematurely withdraw from the study for any reason, should undergo final visit procedures (Visit 2, Day 8) as soon as possible.

6.4.10. Study Conclusion

Subjects will be evaluated to determine if they completed all study procedures or if they were discontinued from the study early. If the subject discontinued at any point during the study, the primary reason for withdrawal should be recorded in the CRF by selecting one of the options below.

- Subject did not meet study criteria
- Protocol violation
- Withdrawal of informed consent
- Unblinding of the subject
- Subject lost to follow-up
- Pregnancy
- Death
- Other

The site personnel will contact IRT to close out of the subject. Subject will be discharged.

Document Name	CCI	Protocol B_Final_Amendment 4_Clean_QA Review		
Type	Version	Document Identifier	Effective Date	
elido_clinical_doc	1.0; CURRENT; Most-Recent; Effective	090032d580d43d4b	19-May-2017 09:57:58	
Reason For Issue	Auto Issue			

7. SAFETY ASSESSMENTS

7.1. Definitions of an Adverse Event and Serious Adverse Event

7.1.1. Adverse Events

The Investigator or site staff will be responsible for detecting, documenting and reporting events that meet the definition of an AE or SAE.

Adverse Event Definition:

- An AE is any untoward medical occurrence in a patient or clinical investigation subject, temporally associated with the use of an investigational or washout product, whether or not considered related to the investigational or washout product.
- NOTE: An AE can therefore be any unfavorable and unintended sign (including an abnormal laboratory finding), symptom, or disease (new or exacerbated) temporally associated with the use of an investigational or washout product.

Events meeting AE definition include:

- Any abnormal laboratory test results (if applicable) or other safety assessments, including those that worsen from baseline, and felt to be clinically significant in the medical and scientific judgment of the Investigator.
- Exacerbation of a chronic or intermittent pre-existing condition including either an increase in frequency and/or intensity of the condition.
- New condition(s) detected or diagnosed after study product administration even though it may have been present prior to the start of the study.
- Signs, symptoms, or the clinical sequelae of a suspected interaction.
- Signs, symptoms, or the clinical sequelae of a suspected overdose of either study product or a concomitant medication (overdose per se will not be reported as an AE/SAE).

Events NOT meeting definition of an AE include:

- Any clinically significant abnormal laboratory findings (if applicable) or other abnormal safety assessments which are associated with the underlying disease, unless judged by the Investigator to be more severe than expected for the subject's condition.
- The disease/disorder/ condition being studied or expected progression, signs,

Document Name	CCI	Protocol B_Final_Amendment 4_Clean_QA Review		
Type	Version	Document Identifier	Effective Date	
elido_clinical_doc	1.0; CURRENT; Most-Recent; Effective	090032d580d43d4b	19-May-2017 09:57:58	
Reason For Issue	Auto Issue			

or symptoms of the disease/disorder being studied, unless more severe than expected for the subject's condition..

- Medical or surgical procedure (e.g., endoscopy, appendectomy): the condition that leads to the procedure is an AE.
- Situations where an untoward medical occurrence did not occur (social and/or convenience admission to a hospital).
- Anticipated day-to-day fluctuations of pre-existing disease(s) or condition(s) present or detected at the start of the study that do not worsen.

7.1.2. Serious Adverse Events

Serious Adverse Event is defined as any untoward medical occurrence that, at any dose:

A. Results in death

B. Is life-threatening

NOTE: The term 'life-threatening' in the definition of 'serious' refers to an event in which the subject was at risk of death at the time of the event. It does not refer to an event, which hypothetically might have caused death, if it were more severe.

C. Requires hospitalization or prolongation of existing hospitalization

NOTE: In general, hospitalization signifies that the subject has been detained (usually involving at least an overnight stay) at the hospital or emergency ward for observation and/or treatment that would not have been appropriate in the physician's office or out-patient setting. Complications that occur during hospitalization are AEs. If a complication prolongs hospitalization or fulfills any other serious criteria, the event is serious. When in doubt as to whether "hospitalization" occurred or was necessary, the AE should be considered serious.

Hospitalization for elective treatment of a pre-existing condition that did not worsen from baseline is not considered an AE.

D. Results in disability/incapacity

NOTE: The term disability means a substantial disruption of a person's ability to conduct normal life functions.

This definition is not intended to include experiences of relatively minor medical significance such as uncomplicated headache, nausea, vomiting, diarrhea, influenza, and accidental trauma (e.g. sprained ankle) which may interfere or prevent everyday life functions but do not constitute a substantial disruption.

E. Is a congenital anomaly/birth defect

F. Other Situations

- Medical or scientific judgment should be exercised in deciding whether reporting is appropriate in other situations, such as important

Document Name	CCI	Protocol B_Final_Amendment 4_Clean_QA Review	
Type	Version	Document Identifier	Effective Date
elido_clinical_doc	1.0; CURRENT; Most-Recent; Effective	090032d580d43d4b	19-May-2017 09:57:58
Reason For Issue	Auto Issue		

medical events that may not be immediately life-threatening or result in death or hospitalization but may jeopardize the subject or may require medical or surgical intervention to prevent one of the other outcomes listed in the above definition. These should also be considered serious.

- Examples of such events are invasive or malignant cancers, intensive treatment in an emergency room or at home for allergic bronchospasm, blood dyscrasias or convulsions that do not result in hospitalization or development of drug dependency or drug abuse or reports of spontaneous abortion.

7.2. Recording Adverse Events and Serious Adverse Events

Recording of adverse events and serious adverse events:

- The Investigator or site staff will be responsible for detecting, documenting and reporting events that meet the definition of an AE or SAE. The Investigator or site staff will then record all relevant information regarding an AE/SAE in the CRF.
- There may be instances when copies of medical records for certain cases are requested by GSK. In this instance, all subject identifiers, with the exception of the subject number, will be blinded on the copies of the medical records prior to submission to GSK.
- The Investigator will attempt to establish a diagnosis of the event based on signs, symptoms, and/or other clinical information. In such cases, the diagnosis will be documented as the AE/SAE and not the individual signs/symptoms. Clinical AEs will be described by diagnosis and not by symptoms when possible (e.g., upper respiratory tract infection, seasonal allergy, etc. instead of runny nose).
- AEs will be collected from the start of the investigational product and until 5 days following last administration of the study product.
- SAEs will be collected over the same time period as stated above for AEs. However, any SAEs assessed as related to study participation (e.g., investigational product, protocol mandated procedures, invasive tests, or change in existing therapy) or related to a GSK concomitant medication will be recorded from the time a subject consents to participate in the study up to and including any follow-up contact.
- Medical conditions reported prior to the time period for reporting AEs/SAEs should be recorded as part of the subject's medical history.

7.3. Evaluating Adverse Events and Serious Adverse Events

Assessment of Intensity:

The Investigator or designee will make an assessment of intensity for each AE and

Document Name	CCI	Protocol B_Final_Amendment 4_Clean_QA Review		
Type	Version	Document Identifier	Effective Date	
elido_clinical_doc	1.0; CURRENT; Most-Recent; Effective	090032d580d43d4b	19-May-2017 09:57:58	
Reason For Issue	Auto Issue			

SAE reported during the study and will assign it to one of the following categories:

- Mild: An event that is easily tolerated by the subject, causing minimal discomfort and not interfering with everyday activities.
- Moderate: An event that is sufficiently discomforting to interfere with normal everyday activities
- Severe: An event that prevents normal everyday activities. - an AE that is assessed as severe will not be confused with an SAE. Severity is a category utilized for rating the intensity of an event; and both AEs and SAEs can be assessed as severe.

Note: An event is defined as 'serious' when it meets at least one of the pre-defined outcomes as described in the definition of an SAE.

Assessment of Causality:

- The Investigator is obligated to assess the relationship between study product and the occurrence of each AE/SAE.
- A "reasonable possibility" is meant to convey that there are facts/evidence or arguments to suggest a causal relationship, rather than a relationship cannot be ruled out.
- The Investigator will use clinical judgment to determine the relationship.
- Alternative causes, such as natural history of the underlying diseases, concomitant therapy, other risk factors, and the temporal relationship of the event to the study product will be considered and investigated.
- The Investigator will also consult the Investigator Brochure (IB) and/or Product Information, for marketed products, in the determination of his/her assessment.
- For each AE/SAE the Investigator **must** document in the medical notes (source document) or CRF that he/she has reviewed the AE/SAE and has provided an assessment of causality.
- There may be situations when an SAE has occurred and the Investigator has minimal information to include in the initial report to GSK. However, it is **very important that the Investigator always make an assessment of causality for every event prior to the initial transmission of the SAE data to GSK.**
- The Investigator may change his/her opinion of causality in light of follow-up information, amending the SAE data collection tool accordingly.
- The causality assessment is one of the criteria used when determining regulatory reporting requirements.

7.4. Reporting Adverse Events and Serious Adverse Events

AE Reporting to GSKCH:

- AEs will be recorded in the AE section of the CRF.
- Medical conditions recorded by the subject on a diary card or similar

Document Name	CCI	Protocol B_Final_Amendment 4_Clean_QA Review	
Type	Version	Document Identifier	Effective Date
elido_clinical_doc	1.0; CURRENT; Most-Recent; Effective	090032d580d43d4b	19-May-2017 09:57:58
Reason For Issue	Auto Issue		

document that meet the definition of an AE must also be recorded in the AE section of the CRF, if not previously well-characterized by the Investigator in the subject's medical history.

- AEs elicited by the Investigator in a standard manner at the study visits should also be recorded in the AE section of the CRF. The Investigator or designee must ask the subject the following question during each visit including any follow-up visits: *"Have you felt unwell, experienced any symptoms or taken any medication (since your last visit) (today) (since your last dose) (since the last session)?"*
- The medically qualified Investigator should review adverse events in a timely manner; this review should be documented in writing in the source document or in the CRF.
- After the study is completed at a given site, and the site has received their study data on Compact Discs (CDs), the electronic data collection tool will be removed from the internet to prevent the entry of new data or changes to existing data.

SAE Reporting to GSKCH:

A paper copy of the SAE form provided in the Investigator study master file should be completed as fully as possible.

It is essential to enter the following information:

- Protocol and subject identifiers
- Subject's demography
- Description of events, with diagnosis if available
- Investigator opinion of relationship to study product (see Section 8.3.)
- Criterion for seriousness.

The following are desirable and are of particular relevance for Investigator and GSKCH assessment of the SAE report:

- Date of onset of AE
- Date AE stopped, if relevant
- Study product start date
- Study product end date if relevant
- Action taken on study product
- Outcome if known

The SAE form, completed as fully as possible, must be faxed to PPD within 24 hours of awareness at the following fax number:

SAE Contact Information

PPD Hotline: PPD

PPD Fax: PPD

Document Name	CCI	Protocol B_Final_Amendment 4_Clean_QA Review		
Type	Version	Document Identifier	Effective Date	
elido_clinical_doc	1.0; CURRENT; Most-Recent; Effective	090032d580d43d4b	19-May-2017 09:57:58	
Reason For Issue	Auto Issue			

PPD will then email the SAE form to the Case Management Group, Global Clinical Safety and Pharmacovigilance at GSK, with copy to the appropriate GSKCH Study Manager as soon as possible, but not later than 1 business day after study site personnel learn of the event. The GSKCH Study Manager will be responsible for forwarding the SAE form to the Medical Director responsible for the study and other GSKCH personnel as appropriate via email.

The initial report will be followed up with more information as relevant, or as requested by the GSKCH study manager.

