8.4. Processing Patient Reported Outcomes

Patient reported outcome (PRO) data will be collected directly into an electronic diary (e-diaries). AEs and concomitant medications entered into the e-diary will be transcribed into the eCRF. Data from the e-diaries will be extracted and loaded in a secured web portal, for the CRO handling Data Management to perform necessary reconciliation with the study data in the Clinical Data Management system. The process for reconciliation will be handled the same way as external data below. The e-diary data will eventually be merged with the Study Data sets.

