9.3.4. Safety Analyses

Safety variables (incidence of adverse events, and vital signs) will be summarized for the Safety population. All tables will be presented by treatment arm.

Treatment emergent adverse events, i.e. AEs that start or worsen during the treatment period (on or after first study treatment administration), will be summarized by presenting the number and percentage of subjects having any AE, any AE in each MedDRA System Organ Class (SOC) and having each individual AE (using MedDRA preferred term). The subset of AEs suspected of a relationship to study treatment will be presented similarly. All treatment-emergent AEs will also be tabulated by severity. Any other information collected (e.g. action taken, duration, outcome) will be listed.

For the summary by severity, subjects who have multiple occurrences of the same AE will be classified according to the worst reported severity of the AE. Similarly, for the summary by treatment relationship, the AE will be classified according to the closest relationship.

Vital signs (blood pressure, pulse, respiration rate, and body temperature) and their change from baseline will be summarized with descriptive statistics.

Document Name	CCI	Protocol B_Final_Amendment 4_Clean_QA Review	
Type	Version	Document Identifier	Effective Date
elido_clinical_doc	1.0; CURRENT; Most-Recent; Effective	090032d580d43d4b	19-May-2017 09:57:58
Reason For Issue	Auto Issue		

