9.1.1. Incidence of Adverse Events

Treatment-emergent adverse events (TEAE) , i.e. AEs that start or worsen during the treatment period (on or after first study medication administration), will be summarized by presenting the number and percentage of subjects having any AE, any AE in each MedDRA System Organ Class (SOC) and having each individual AE (using MedDRA preferred term (PT)). At each level of subject summarization, a subject is counted once if the subject reported one or more events. Percentages will be calculated out of the number of subjects in the Safety population. The number of events will also be presented in the table.

The summary of TEAEs will be presented in descending order from the SOC with the highest total incidence (that is, summed across all treatment groups) to the SOC with the lowest total incidence. If the total incidence for any two or more SOC is equal, the SOC will be presented in alphabetical order. Within each SOC, the PTs will be presented in descending order, in the same manner as SOC.

The incidence of TEAE between treatment groups is compared using a frequency table for Safety population.

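### The diary bullet in Protocol 7.4 can be read to keep worsened pre-existing conditions off the AE page, in conflict with 7.1.1, 7.2, 8.4 and the TEAE definition

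*Protocol*

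**What the plan says.** Protocol 7.4 opens its AE list with a rule that carries no condition: "AEs will be recorded in the AE section of the CRF". The next bullet deals with conditions that subjects write in a diary card or similar document. Those that satisfy the AE definition "must also be recorded in the AE section of the CRF, if not previously well-characterized by the Investigator in the subject's medical history". The bullet after that covers AEs elicited by a standard question at visits, and has no medical-history exception.

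Protocol 7.1.1 counts as an AE: "Exacerbation of a chronic or intermittent pre-existing condition including either an increase in frequency and/or intensity of the condition". Among the things that are not AEs it lists: "Anticipated day-to-day fluctuations of pre-existing disease(s) or condition(s) present or detected at the start of the study that do not worsen".

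On recording, Protocol 7.2 says: "The Investigator or site staff will then record all relevant information regarding an AE/SAE in the CRF". On e-diary data, Protocol 8.4 says: "AEs and concomitant medications entered into the e-diary will be transcribed into the eCRF". Neither mentions medical history as a reason to leave an AE out.

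On tabulation, Protocol 9.3.4 defines treatment-emergent events as "AEs that start or worsen during the treatment period (on or after first study treatment administration"), and SAP 9.1.1 as "AEs that start or worsen during the treatment period (on or after first study medication administration").

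**The concern.** The diary bullet applies its exception after the AE definition has been met. An exception placed there cannot be doing the ordinary job of screening out stable history, because the definition has already done that. What is left for it to act on is mainly a known condition that worsened on treatment.

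The e-diary is where subjects record AEs at home on Days 2 to 7, and the only scheduled visit after Day 1 is on Day 8. Protocol 9.2.4 bases the safety assessment on the comparison of AE incidence between arms. Medication for controlled chronic disease is allowed (Protocol 3.2), so some subjects will enter with known conditions. If sites differ on whether a diary report of worsening goes to the AE page, the incidence depends partly on which section a site follows, and some events may never reach the table.

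**Working it through.** No formula applies to the conflict itself. The check compares the clause with the AE definition, the other recording rules and the tabulation rule.

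**Step 1. What the exemption can act on.** Take the kinds of diary entry in turn, under Protocol 7.1.1 and 7.2.

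| Diary entry | AE under 7.1.1? | Exempt under the 7.4 diary bullet, read literally? |
|---|---|---|
| New condition, not in the history | Yes | No, since nothing was characterized beforehand |
| Known condition, usual fluctuation, no worsening | No | Not relevant; the bullet covers only AEs |
| Expected course of the cold | No | Not relevant, for the same reason |
| Known condition, more frequent or more intense | Yes | Yes, if the history is taken to have characterized it |

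The last row is the main class on which the exemption has any effect. Conditions reported before the AE collection period are already sent to the medical history by 7.2, so the clause is not needed for them either.

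**Step 2. What the other recording rules say about that class.**

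- Protocol 7.2: record in the CRF, no exception.
- Protocol 7.4, first bullet: record in the AE section, no exception.
- Protocol 7.4, visit-elicited bullet: record in the AE section, no exception.
- Protocol 8.4: transcribe e-diary AEs, no exception.
- Protocol 6.4.4: clinically relevant new or worsening nasal findings at Day 8 go to the AE page.
- Protocol 7.4, diary bullet: can be read as not requiring entry.
- SAP Appendix C: an AE left out of the AE section of the eCRF is a deviation, rated not significant.

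The diary bullet stands alone against the rest, and nothing in either document says which rule governs.

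**Step 3. What the tables need.** Both TEAE definitions include worsening. They tabulate what has been recorded and are not recording rules themselves. An AE that never reaches the AE page cannot be counted in a table that is meant to include it.

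**Step 4. When an event would actually be missing.** All of these must hold: the event is a worsening of a documented condition; the site takes the clause literally and does not apply 7.2 or 8.4; and the subject's answer to the AE question at Day 8, or the examinations there, do not bring it out. Serious events have a separate reporting route in 7.4.

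**Step 5. Size.** The documents give no AE rate, no count of subjects with pre-existing conditions and no expected number of diary-only exacerbations. The number lost cannot be estimated. The only figure available is the weight of one subject: with the planned 85 per arm (Protocol 9.1, SAP 4.2), 1/85 = 0.0118, or about 1.2 percentage points of that arm's incidence, taking the Safety population as all 85.

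**The case against.** The strongest answer is that the clause does not say that presence in the medical history is enough. It requires that the investigator had characterized the condition well beforehand. A new rise in frequency or intensity after the first dose was, on a fair reading, not characterized beforehand, so the clause need not exempt it. This stands as a possible reading. It does not remove the point, because two sites can reasonably read the same words in opposite ways.

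The second answer is that several safeguards exist: the unconditional duties in 7.2, 8.4 and the first bullet of 7.4, the AE question at each visit, the Day 8 physical and nasal examinations, and the end-of-study visit for early terminators. This also stands, and it limits the likely loss. Entry criteria narrow the pool further by requiring good general health and excluding persistent asthma, perennial rhinitis and relevant nasal disease, and treatment lasts only 7 days.

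A reader might go further and infer that the plan removes all worsened pre-existing conditions from the CRF, so that a true difference between arms in such events would be tabulated as none in either arm. The documents do not support that. It would require every site to follow the exemption against three other rules, every event to be recorded only in the diary, and the Day 8 question to recover none. Nor do they support any assumed percentage of affected subjects, or a claim that the product is likely to worsen such conditions.

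**Conclusion.** The point holds as an internal contradiction in the safety-recording rules. On a literal reading, the diary bullet in Protocol 7.4 exempts mainly the exacerbations that 7.1.1 defines as AEs and that both TEAE definitions include, and it disagrees with 7.2, 8.4 and the first bullet of its own list. The consequence is possible inconsistency between sites and possible under-counting of non-serious worsening events, not a settled omission. The size is unknown. The conclusion that the text conflicts needs no event rate. The conclusion that events could be lost assumes that at least some sites follow the exemption and that Day 8 does not recover every such event. Efficacy analyses are not affected. The change is worth making because AE incidence is the trial's main safety comparison and the correction is small.

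**What to change.** In Protocol 7.4, delete the medical-history exemption from the diary bullet. If the sponsor prefers to keep a reminder about stable history, limit it, for example: *Diary conditions that meet the AE definition are entered in the AE section of the CRF. A condition documented in the medical history is left out only if it has not increased in frequency or intensity since the first dose (see 7.1.1).* The second form repeats what 7.1.1 already implies, but it ends the ambiguity.

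Leave 8.4 unchanged. It is unconditional now, and adding the exemption there would weaken a rule that works. The TEAE definitions in Protocol 9.3.4 and SAP 9.1.1 need no change.

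The cost is one clause in a protocol amendment and a short note to sites. There may be a few more AE entries, so reported AE incidence may rise slightly.
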